#### 4.2.2 Restrictions

##### 4.2.2.1 Restrictions regarding concomitant treatment

For everolimus: Everolimus is a substrate of CYP3A4, and also a substrate and moderate inhibitor of PgP. Systemic concomitant strong CYP3A4 inhibitors and PgP inhibitors should not be used with everolimus. (refer to [Appendix 3](#) for a list of examples).

Use caution when co-administration of moderate CYP3A4 inhibitors or PgP inhibitors cannot be avoided (refer to [Appendix 3](#) for a list of examples). If patients require co-administration of a moderate CYP3A4 or PgP inhibitor, dose reduction to 5 mg daily or 2.5 mg daily may be considered. Due to between subject variability the recommended dose adjustments may not be optimal in all individuals, therefore close monitoring of side effects is recommended. If the moderate inhibitor is discontinued, consider a washout period of at least 2 to 3 days (average elimination time for most commonly used moderate inhibitors) before the everolimus dose is returned to the dose used prior to initiation of the co-administration.

Avoid the use of concomitant potent CYP3A4 inducers (e.g. rifampicin, phenytoin, carbamazepine, phenobarbital, dexamethasone or St. John's wort). If patients require co-administration of a potent CYP3A4 inducer, an everolimus dose increase from 10 mg daily up to 20 mg daily should be considered using 5 mg increments or less applied on Day 4 and 8 following start of the inducer. If treatment with the inducer is discontinued, consider a washout period of at least 3 to 5 days (reasonable time for significant enzyme de-induction), before the everolimus dose is returned to the dose used prior to initiation of the co-administration.

St.John's Wort may decrease everolimus exposure unpredictably and therefore should be avoided.

For exemestane: Exemestane is a substrate of CYP3A4. Pharmacokinetic study showed that co-medications that induce CYP3A4 (e.g.; rifampicin, phenytoin, carbamazepine,

Proprietary confidential information.

© 2016 Boehringer Ingelheim International GmbH or one or more of its affiliated companies. All rights reserved.

This document may not - in full or in part - be passed on, reproduced, published or otherwise used without prior written permission.

phenobarbital, dexamethasone or St. John's wort) may significantly decrease exposure to exemestane.

Since the clinical relevance of this interaction has not been evaluated, the co-administration of drugs, known to induce CYP3A4 may reduce the efficacy of exemestane.

Exemestane does not inhibit any of the major CYP isoenzymes, including CYP 1A2, 2C9, 2D6, 2E1, and 3A4. Nevertheless, exemestane should be used cautiously with drugs that are metabolised via CYP3A4 and have a narrow therapeutic window.

In order to effectively assess the pharmacokinetics of exemestane, everolimus and BI 836845 and to investigate potential alterations of pharmacokinetics during co-administration, **strong and moderate CYP3A4 inhibitors/inducers and/or strong and moderate P-gp inhibitors are prohibited during the run-in period and the first treatment course at the Phase I part** (refer to [Appendix 3](#) for a list of examples). Switching to a different class of drug that is not a strong or moderate CYP3A4 inhibitor/inducer and/or strong or moderate P-gp inhibitor at least 14 days prior to the run-in period is permitted.

Starting from Day 1 of Course 2 of the Phase I part and Day 1 of Course 1 of the Phase II part, follow the respective drug package insert/SPC when considering concomitant treatment with CYP3A4/PgP inhibitors/inducers.

Antiplatelet medications (e.g. acetylsalicylic acid) should be discontinued 7 days prior to tumor biopsy. Anticoagulant medications should be discontinued prior to tumor biopsy. Warfarin should generally be discontinued at least 5 days prior to tumor biopsy. In all patients, the risk of discontinuing antiplatelet and/or anticoagulant medications must be weighed against the (potential) risk of bleeding during/after biopsy. These medications may be restarted after tumor biopsy at the discretion of the investigators.

In addition, the following concomitant treatments are not allowed during the study:

- 1) Chronic concomitant bisphosphonate therapy for the prevention of bone metastases (the use of any other agent for the prevention of bone metastasis is not allowed during the study).
- 2) Investigational or commercial anticancer treatment and/or standard chemo-, immunotherapy, targeted therapy, biological response modifiers, or endocrine therapy other than exemestane
- 3) Growth hormones or growth hormone inhibitors
- 4) Hormone replacement therapy, topical estrogens (including any intra-vaginal preparations), megestrol acetate and selective estrogen-receptor modulators (e.g. raloxifene)
- 5) Prolonged systemic corticosteroid treatment, except for topical applications (e.g. rash), inhaled sprays (e.g. obstructive airways diseases), eye drops or local injections

Proprietary confidential information.

© 2016 Boehringer Ingelheim International GmbH or one or more of its affiliated companies. All rights reserved.

This document may not - in full or in part - be passed on, reproduced, published or otherwise used without prior written permission.

(e.g. intraarticular) should not be given. A short duration (<2 weeks) of systemic corticosteroids is allowed (e.g. chronic obstructive pulmonary disease, anti-emetic)

- 6) Hematopoietic growth factors (e.g. erythropoietins, G-CSF and GM-CSF) are not to be administered prophylactically. Use of these should be reserved to cases of severe neutropenia and anemia as per the labelling of these agents
- 7) The use of concomitant medications that prolong the QT/QTc interval (refer to website [crediblemeds.org](http://crediblemeds.org) for the list of medications) should be avoided, except in those cases where treatment is necessary after a risk-benefit evaluation by the investigator and provided that the drug in question cannot be substituted by any other agent.

It is to be noted that

- 1) Everolimus may affect the response to vaccinations making it less effective. Live vaccines should be avoided while a patient is treated with everolimus.
- 2) Lipid-lowering drugs may be given in case of hyperlipidemia according to local best clinical practice.
- 3) Antihyperglycemic drugs may be given in case of hyperglycemia according to local best clinical practice.

Otherwise, the use of other concomitant medication/therapy deemed necessary for the care of the patient is allowed.

#### 4.2.2.2 Restrictions on diet and life style

Patients should avoid grapefruit and grapefruit juice while treated on everolimus. Patients also have to show up in fasting condition at the site when blood draw for safety lab is required.

Everolimus and exemestane tablets should be administered with a large glass of water (~ 240 mL). Patients should be advised not to eat within 2 hours after drug administration and not to drink within 1 hour after drug intake.

For specific instructions on food and drug intake during the Run-in period and up to C1D8 of the phase I part for DDI analysis, refer to [section 4.1.4.1.4](#).

### 4.3 TREATMENT COMPLIANCE

The study medications will be given in accordance with the protocol and the instructions of a site investigator. The investigator should instruct the patient to take the study drugs exactly as prescribed to promote compliance.

Proprietary confidential information.

© 2016 Boehringer Ingelheim International GmbH or one or more of its affiliated companies. All rights reserved.

This document may not - in full or in part - be passed on, reproduced, published or otherwise used without prior written permission.

#### **4.3.1 BI 836845**

BI 836845 will be administered as a single infusion under supervision of the investigator or dedicated study personnel. In the event that the full dose of BI 836845 is not administered to the patient, it must be documented and explained.

A maximum of three BI 836845 infusions may be skipped for the recovery from AEs. Missing BI 836845 treatment for any other reasons is considered non-compliant.

#### **4.3.2 Everolimus and exemestane**

Patients should be given appropriate number of everolimus and exemestane tablets to be self-administered. During the run-in phase and up to the Visit 3 (Day 8±1) in first treatment course of the Phase I part, the patient will be requested to record each dose of medication in a diary. The medication diary will be returned to clinic staff at the end of run-in phase and at Visit 3 of the first treatment course.

Patients will be asked to bring the remaining investigational oral medication everolimus on Day 1 of each treatment course to the investigator site. Compliance of investigational everolimus will be assessed by the investigator and/or study personnel using pill counts and information provided by the patient or caregiver. This information and discrepancies between the number of tablets remaining and the calculated number of tablets the patients should have taken must be documented and explained. The compliance of exemestane and non-investigational everolimus (if applicable) will be assessed following the local regulation and practice, using either patient diary, pill counts, information provided by the patient or caregiver or the combination of any of them. If a patient is eligible for further treatment, medications of everolimus and exemestane must be made available.

During the run-in phase, everolimus and exemestane must be taken daily without skipping any dose. If doses of everolimus or exemestane are missed during run-in period, treatment with BI 836845 may commence and the reason for not taking everolimus and exemestane as per protocol requirement must be documented in the eCRF (refer to [section 3.3.4.1](#)). During the treatment phase, a maximum of 25% of the planned doses per four-week period may be missed for reasons other than recovering from AEs; patients who miss everolimus/exemestane treatment more frequently are considered non-compliant.

#### **4.3.3 Compliance Assessment**

Patients who do not attend a minimum of 75% of scheduled study visits, unless due to exceptional circumstances, should be discussed with BI clinical monitor and be evaluated for compliance.

The investigator and/or the sponsor can withdraw a patient from the study in the event of serious and persistent non-compliance which jeopardizes the patient's safety or render study results.

## 4.4 MANAGEMENT OF EXPECTED ADVERSE EVENTS

The following recommendation should be followed unless institutional guidelines can be implemented based on the investigator's judgement. The EU Summary of product characteristics or prescribing information of respective country for everolimus and exemestane should also be referred to when managing drug related adverse events.

In everolimus SPC, non-infectious pneumonitis, infections, hypersensitivity reactions, concomitant use of angiotensin-converting enzyme inhibitors, oral ulceration, renal failure events, and some lab tests and monitoring are described under "Special warnings and precautions for use". For updated information regarding warning and precautions of everolimus and exemestane, please refer to the most current version.

### 4.4.1 Management of oral mucositis

#### 4.4.1.1 Mouth care

- Routine and systematic oral hygiene is extremely important to reduce the incidence and severity of the side effects of cancer treatment.
- Correct oral hygiene should be maintained with daily brushing of the teeth, tongue and gums, performed after meals and before going to bed, using a non-irritant toothpaste, a soft toothbrush and dental floss to clean between the teeth. This should be followed by rinsing the mouth with a mouthwash.
- Mouthwashes eliminate food particles that can accumulate and favour bacterial growth. The preferred solutions are normal saline, sodium bicarbonate, or a mixture of the two, to be used after each meal and before going to bed; solutions containing alcohol should be avoided as they dehydrate the mucosa. If the mucosa is ulcerated, do not use hydrogen peroxide solution as this will interfere with the formation of granulation tissue and healing of the ulcer. Do not use products that contain alcohol, glycerine or lemon, or toothpastes with an abrasive action.
- Dental prostheses should be cleaned and brushed in the same way as the mouth, and at night should be left in 1% sodium hypochlorite solution (if they contain no metal) or in a solution of povidone iodine.
- The lips must be maintained in a perfect state of hydration using lip balms (cocoa butter), methylcellulose solutions, moisturising cream or olive oil. Avoid using petroleum jelly or glycerine because of their dehydrating effects on the lip tissue.
- Chlorhexidine is an antiseptic with a broad antimicrobial spectrum. It has a bacteriostatic action and is particularly active against gram-positive micro-organisms; it is sporostatic and fungistatic (activity against candida). It has a rapid effect and, in addition, presents considerable persistence and residual adherence. Due to its cationic nature, it has the property of binding to the oral mucosa. It has been used in the form of 15 ml of 0.12% chlorhexidine mouthwash 2-3 times a day.

Proprietary confidential information.

© 2016 Boehringer Ingelheim International GmbH or one or more of its affiliated companies. All rights reserved.

This document may not - in full or in part - be passed on, reproduced, published or otherwise used without prior written permission.

- Avoid foods that trigger pain: acids, spicy and hot foods. Attempt to eat a soft diet and increase the intake of cold and nutritious fluids.
- Avoid irritants such as alcohol and tobacco

#### 4.4.1.2 Treatment of established mucositis

- Lidocaine is an amide-type local anaesthetic that is widely used both topically and parenterally. In the management of mucositis, it can be useful for the treatment of pain. It is administered locally in the form of a gel or solution. Apply 1% lidocaine viscous to ulcers before each meal.
- Nystatin is an antifungal (fungistatic) agent with a broad spectrum. Nystatin suspension has been studied as prophylaxis against candida in patients on treatment with antineoplastic and/or immunosuppressant drugs. Apply after the main meals if there are signs of candidal superinfection of mucositis.

Corticosteroids, in the case of mucositis, reduce the inflammatory reaction that occurs in this condition, probably by inhibiting the production of leukotrienes and prostaglandins.

- Triamcinolone acetonide 0.1% in orabase qsp 30 g or
- Hydrocortisone 1% in orobase qsp 50 g

Applications are performed 2-3 times a day with the recommendation not to eat or drink for 30 minutes after the application to facilitate its adherence to the mucosa.

In case of no improvement of mucositis, additional therapy may be added:

- Fluconazol oral 100 mg daily in case of no improvement with topical antifungal treatment with nystatin.

Please note that fluconazole is a moderate inhibitor of CYP3A4, which may potentially have an impact on metabolism of everolimus and exemestane.

- Systemic antiherpetic therapy (ie Famvir 750 mg/d for 7 days otherwise Aciclovir oral or iv.) at investigator's discretion.

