## 5.2.6 Dose limiting toxicity (DLT)

The primary endpoints of the Phase I part are occurrence of Dose Limiting Toxicity (DLT) and determination of MTD.

A dose limiting toxicity (DLT) in this study is defined as an adverse event or laboratory abnormality which 1) is considered related to study drug and 2) meets any of the following criteria:

- CTCAE Grade 3 hyperglycemia lasting > 48 hours
- CTCAE grade 4 hyperglycemia
- CTCAE Grade  $\geq 3$  stomatitis (oral mucositis) despite appropriate supportive care
- CTCAE Grade  $\geq 3$  thrombocytopenia lasting  $\geq 7$  days or thrombocytopenia associated with active bleeding or requiring platelet transfusion
- CTCAE Grade  $\geq 4$  decreased platelet count

Proprietary confidential information.

© 2016 Boehringer Ingelheim International GmbH or one or more of its affiliated companies. All rights reserved.

This document may not - in full or in part - be passed on, reproduced, published or otherwise used without prior written permission.

- CTCAE grade  $\geq$  3 febrile neutropenia and/or documented infection with ANC  $<1.0 \times 10^9/L$
- CTCAE Grade 4 decreased neutrophil count lasting  $\geq$  7 days
- AST or ALT  $> 5 \times$  ULN (for baseline AST/ALT  $\leq$  ULN) or  $>$  (baseline value + 4x ULN) (for baseline AST/ALT  $>$  ULN)
- CTCAE grade  $\geq$  3 diarrhea, nausea, or vomiting despite adequate supportive care
- CTCAE Grade  $\geq$  3 skin rash despite adequate supportive care measures
- CTCAE Grade  $\geq$  3 fatigue/asthenia lasting for more than seven days
- Grades 3 to 4 hyperlipidemia (total cholesterol  $> 400$  mg/dL or triglycerides  $> 500$  mg/dL) not improving despite appropriate treatment for 4 weeks
- Any AE necessitating a 2-week treatment interruption
- All other toxicities of CTCAE Grade  $\geq$  3 (except alopecia, allergic reaction, infusion reaction and those mentioned above)
- Any other study drug related toxicity considered significant enough to be qualified as DLT in the opinion of the investigators (e.g. AE which not defined as DLT but requires dose reduction according to everolimus label), and confirmed by the safety review with the BI clinical monitor and BI project physician (TMM), will be reported as a DLT

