## 10.3 LIST OF CYP3A4 INHIBITORS, INDUCERS AND LIST OF INHIBITORS OF P-GLYCOPROTEIN

### 10.3.1 Examples of CYP 3A4 inhibitors and inducers

CYP3A4 Inhibitors	CYP3A4 Inducers

Strong inhibitors:
 
atazanavir, boceprevir, ciclosporin, clarithromycin, conivaptan, darunavir, grapefruit juice*, indinavir, itraconazole, ketoconazole, lopinavir/ritonavir, mibefradil, nefazodone, nelfinavir, osaconazole, posaconazole, ritonavir, saquinavir, telaprevir, telithromycin, voriconazole
 
Moderate inhibitors:
 
amprenavir, aprepitant, atazanavir, ciprofloxacin, crizotinib, darunavir, diltiazem, erythromycin, fluconazole, fosamprenavir, grapefruit juice*, imatinib, ritonavir, verapamil
 
* The effect of grapefruit juice varies widely and is preparation-dependent.
	
Strong inducers:
 
carbamazepine, phenytoin, rifampin/rifampicin, rifabutin, rifapentine, phenobarbital, St. John's wort**
 
** The effect of St. John's wort varies widely and is preparation-dependent.
 
Moderate inducers:
 
bosentan, corticosteroids (e.g. dexamethasone, prednisone, prednisolone), phenobarbital, efavirenz, etravirine, modafinil, nafcillin, nevirapine

Proprietary confidential information.

© 2016 Boehringer Ingelheim International GmbH or one or more of its affiliated companies. All rights reserved.

This document may not - in full or in part - be passed on, reproduced, published or otherwise used without prior written permission.

As the information may evolve, it is important for the investigator to assess such status on concomitant therapies and contact BI clinical monitor in case of questions.

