Table 6.2 : 1 Important protocol violations (cont.)

Category/ Code	Description	Requirements	Excluded from
C2 [2]	Trial medication not given according to protocol	
Dose reduction scheme not followed (see CTP section 4.1.4.3);
 
Administration of trial medication(s) not compliant.
 
Indicated by medical review (i.e. where Administration of xentuzumab according to the protocol = 'No' and associated comments, or compliance data from Exemestane/Everolimus with associated comments)
 
Please note: This excludes the investigational treatment given outside the boundaries specified in the CTP (covered in Category C3)
	None
C3 [1]	Infusion time for the investigational treatment outside of CTP specific boundaries	
Infusion duration of xentuzumab given <50 minutes or >200 minutes (Infusion time should be from 60 to 180 minutes, but the thresholds above are accepted).
 
The exact duration of the infusion should be calculated taking interruptions into account.
 
In case of missing administration times, the violation will not be considered important if administration according to protocol = 'Yes'
	None
C4 [2]	Patient assignment not followed	Patients do not receive the initial treatment they were randomised / allocated to	None
C4.1	Randomisation not followed	This applies only for phase II part of the trial	None

Proprietary confidential information © 2018 Boehringer Ingelheim International GmbH or one or more of its affiliated companies

Table 6.2 : 1 Important protocol violations (cont.)

Category/ Code	Description	Requirements	Excluded from
	C4.2	Treatment allocation not followed Treatment taken at C1V1 is not the treatment assigned at screening.	None
D [2]	Concomitant medication		
	D1	Prohibited treatment during trial conduct phase Treatment taken during the treatment period as described in Section 4.2.2.1 of the CTP. For phase Ib part only, during run-in and course 1: CYP3A4 strong inhibitors, CYP3A4 moderate inhibitors, CYP3A4 strong inducers, CYP3A4 moderate inducers, inhibitors of P-glycoprotein	None
E [2]	Missing Data		
	E1	Imaging assessments not done according to CTP instructions Imaging assessment should be performed at Screening and several time points thereafter (see TSAP Section 6.7.2).	None
F [2]	Trial Specific protocol violations		
	F1	Other protocol violations affecting patient rights or safety Manual Protocol Violations (PVs) will be collectively captured.	None

[1] IPV will be derived automatically

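### The mucositis guidance offers oral fluconazole with no Phase I exception, although moderate CYP3A4 inhibitors are prohibited in the Phase I run-in and Course 1

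*Protocol*

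**What the plan says.** Protocol Section 4.4 opens its guidance on expected adverse events with this line: "The following recommendation should be followed unless institutional guidelines can be implemented based on the investigator's judgement". Section 4.4.1.2 covers lidocaine, nystatin and topical corticosteroids, and then says: "In case of no improvement of mucositis, additional therapy may be added". The first item under that line is "Fluconazol oral 100 mg daily in case of no improvement with topical antifungal treatment with nystatin". A note follows: "Please note that fluconazole is a moderate inhibitor of CYP3A4, which may potentially have an impact on metabolism of everolimus and exemestane". Nothing in 4.4.1.2 separates Phase I from Phase II, or Course 1 from later courses.

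Section 4.2.2.1 says that strong and moderate CYP3A4 inhibitors and inducers, and strong and moderate P-gp inhibitors, "are prohibited during the run-in period and the first treatment course at the Phase I part". The stated reason is to allow the pharmacokinetics, and any change in them on co-administration, to be assessed. Label-based rules take over only from Day 1 of Course 2 in Phase I, and from Day 1 of Course 1 in Phase II. The moderate inhibitors in Appendix 10.3.1 include "aprepitant, atazanavir, ciprofloxacin, crizotinib, darunavir, diltiazem, erythromycin, fluconazole".

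SAP Table 6.2: 1, code D1, reads "For phase Ib part only, during run-in and course 1: CYP3A4 strong inhibitors, CYP3A4 moderate inhibitors" and goes on to inducers and P-gp inhibitors. The SAP calls these violations potentially important and excludes no patient because of D1.

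In Protocol Section 5.2.6, a related Grade 3 or higher "stomatitis (oral mucositis) despite appropriate supportive care" is a DLT. Only DLTs in the first 28-day treatment period count for dose finding.

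**The concern.** Stomatitis is a toxicity that the protocol expects the combination might worsen (Section 2.3), and Section 4.4 is where sites are sent to manage it. For mucositis that does not respond, that guidance offers a drug which another section bans in the Phase I run-in and Course 1. The caution next to it reads as advice to take care, not as a reminder of the ban.

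Two assessments are exposed. One is the comparison of everolimus and exemestane pharmacokinetics with and without BI 836845, which the ban exists to protect. The other is attribution of DLTs. Under Section 4.1.3.2 the next cohort depends on whether DLTs relate mainly to BI 836845 or to everolimus, and a drug that inhibits everolimus metabolism blurs that judgement. A smaller gap lies in 5.2.6, which does not say whether supportive care that leaves out a listed but prohibited step still counts as appropriate.

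**Working it through.** The plan states no figure on this point, so the check sets the texts and time windows side by side.

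1. **Is fluconazole covered by the ban?** Yes. Appendix 10.3.1 and the note in 4.4.1.2 both class it as a moderate CYP3A4 inhibitor, and 4.2.2.1 bans that class.

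2. **Do the windows overlap?**
   - Prohibition: 7-day run-in + 28-day Course 1 = 35 days.
   - DLT window (Protocol 5.2.6): 28 days. The share inside the prohibition is 28/28, or all of it.
   - SAP 5.1.1 runs the MTD evaluation period from the first xentuzumab dose to the start of cycle 2. In Phase I the label-based rules also begin on Day 1 of Course 2, so the overlap stays complete if Course 1 runs long.
   - Period marked critical for the drug-interaction analysis (Protocol 4.1.4.1.4): run-in up to Course 1 Day 8 = 7 + 8 = 15 days, all inside the prohibition.

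3. **How strong is the fluconazole wording?** It is permissive. Two conditions come first: nystatin is for signs of candidal superinfection, and fluconazole is for when nystatin has not worked.

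4. **Are sites steered to this text?** Yes. Section 2.3 requires early, proactive management of stomatitis and refers to Section 4.4, and Section 4.1.4.3 does much the same. Section 4.1.4.3 also makes an exception for Phase I Course 1 twice when it discusses label-based dose adjustment. Section 4.4.1.2 makes none.

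5. **Do the documents treat the interaction as relevant?** Yes, without a size. Section 4.2.2.1 allows a lower everolimus dose to be considered when a moderate inhibitor is needed. No exposure ratio is given, so none is calculated here.

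6. **What happens to a DLT that arises on a prohibited inhibitor?** No specific rule applies. The replacement reasons in Protocol 3.3.5 do not name prohibited medication, which leaves only the general category of patients not evaluable for DLT. D1 excludes nobody. Such a DLT would therefore count toward the limit of 1 in 6 unless the case review decided otherwise.

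**The case against.** The best reply is that this is only a missing cross-reference. The ban is specific, limited in time and worded as a prohibition; the fluconazole line is a general option. Section 4.4 also gives way to institutional guidelines. A reader might infer that a site cannot follow both sections. The documents do not support that, because withholding an optional drug satisfies both.

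The second reply is that confounding is already partly handled. The causality assessment in Protocol 5.2.2.1 must weigh concomitant medication. Escalation decisions under 5.2.6 follow discussion between sponsor and investigators in the light of all safety data. Non-evaluable patients can be replaced. D1 cases are reviewed individually, and the Phase Ib safety analysis described in SAP 9.1 included a listing of concomitant therapies. Section 4.1.4.3 also requires BI 836845 and everolimus to be paused once a DLT occurs in Course 1, so the exposure question mainly concerns mucositis that has not yet reached that point. Use within the 15-day interaction period would need superinfection, nystatin failure and fluconazole in quick succession.

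Third, 5.2.6 does not cite 4.4.1.2, so nothing makes fluconazole a required part of appropriate care.

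All of this stands, and it limits the weight of the point. It does not remove the gap: the text that sites are told to use for stomatitis offers a banned drug without mentioning the ban.

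**Conclusion.** The inconsistency is real and modest. Any fluconazole given under 4.4.1.2 during the Phase I run-in or Course 1 is prohibited medication under 4.2.2.1, and the whole 28-day DLT window falls in that period. How often this happened, and how far everolimus or exemestane exposure would move, cannot be taken from the documents.

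Two stronger readings should be resisted.

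- A reader might treat the everolimus reductions to 5 or 2.5 mg mentioned in 4.2.2.1 as a measure of the exposure effect. They are options for moderate inhibitors in general, not an exposure estimate for fluconazole at this dose.
- A reader might conclude that the MTD is unsound and should be recounted without such patients. No document reports such use. A recount would leave 3+3 cohorts below the sizes that their rules assume, with no rule for reading the result.

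The conclusion rests on the protocol revision of 30 March 2016. The SAP refers to a later amendment, dated 15 December 2016, whose text was not available. The Phase Ib interim report is dated 4 August 2015 and recruitment stopped on 28 October 2016. Changing the text therefore cannot alter the dose already chosen; its value is for the record and for trials that reuse this guidance.

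**What to change.** Reconcile Sections 4.4.1.2 and 4.2.2.1 for the Phase I run-in and Course 1, and state in 5.2.6 how the outcome bears on appropriate supportive care for the stomatitis criterion. The sponsor's clinicians decide which instruction stands; this review proposes none.

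In the Phase Ib DLT listing planned in SAP 7.4.1, flag patients who received a CYP3A4 or P-gp inhibitor or inducer listed in Appendix 10.3 from Day -7 to the end of Course 1, with start and stop dates relative to any DLT. Show incomplete dates as undetermined: SAP 6.6 does not impute them, and SAP 7.2 assigns records with both dates missing to the time before study medication.

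The cost is about a sentence in each affected section and one flag in an existing listing. Protocol 4.2.1.3 already collects concomitant medications with start and end dates from consent onward, so no new data are needed.
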